## **12. Potential Risks, Discomforts, Inconveniences, & Precautions:**

### **Potential Risks**

Psychological and social risks are expected to be minimal (e.g., potential embarrassment about answering questions related to adherence).

Venipuncture: Drawing blood from a vein in the lower arm may cause mild pain and occasionally minor bruising at the site of the blood draw. Fainting can also occur. There is a remote chance of infection or peripheral venous phlebitis or thrombosis. For study subjects with diabetes, the requirement of a fasting blood sample may precipitate a temporary blood glucose level that is somewhat lower or higher than usual.

DISCONTINUED AS OF 4/2020. DXA scanning exposes subjects to a small dose of ionizing radiation. This dose of radiation is comparable to that obtained on a transcontinental airplane flight.

Continuous glucose monitoring (CGM). This procedure is routinely used in clinical practice. The main risks of CGM are local irritation from the sensor or tape.

Breach of confidentiality is a risk, although this is highly unlikely as data are used exclusively for research purposes and participants will be provided with information on how risks to confidentiality are minimized (see protection against risks for further details).

### **Adequacy of Protection against Risks**

### **Recruitment and Informed Consent**

For both clinical sites (University of North Carolina, Stanford) we will invite eligible patients to participate in this study by emailing them an introductory letter that describes the study. These letters will be followed with telephone calls to answer questions and encourage participation.

Research staff at the clinical sites will obtain written informed consent from participants. The study consent will explain the purpose of the study and measures taken to protect confidentiality (e.g., the data will not be linked with personal identifying information). A full informed consent protocol will be developed under the guidance of the Institutional Review Boards at each of the three clinical performance sites. Patients will be assured that participation is voluntary and that non-participation will not result in any

consequences to them. In addition, they will be informed that they may withdraw from the study at any time without consequences. Finally, participants will be informed that the data are used exclusively for research purposes, that identifying data will not be released by the investigators to their families or to any other individual or organization, and that any identifying information will be destroyed at the end of the project. Participants will be given adequate time prior to signing the informed consent document to ensure that they have an opportunity to ask and receive answers to any and all questions about study participation.

In soliciting the cooperation of each young adult in our study, we will stress the data safeguards that will be in place to protect the confidentiality of the survey data. Minimizing the risk of disclosure requires careful data safeguards. Most important is the need to prevent the association of an individual's name with sensitive information. We will keep participants' names separate from their survey responses and store the link between names and study identification numbers in a password-protected file that is accessible only to authorized staff at the respective clinical sites.

Participants will have opportunity to provide informed consent following the two-step recruitment process detailed above. For participants who agree to participate and schedule a baseline visit, the study consent form will be mailed or emailed to the participant prior to the scheduled baseline visit, so that the individual has ample time to review it on their own ahead of the visit. Participants will also be provided with instructions on how to use CDART, the data management system that we will employ to house participant data and house self-administered questionnaires. This email will also include a personalized link to a Qualtrics questionnaire, which provides participants the chance to read a consent form specific to completing baseline forms ahead of the in-person visit. If they choose to consent to completing these forms ahead of the visit, study staff will then email them their login information for CDART. These emails will include relevant visit reminders that have been previously reviewed during phone conversations with participants. Prior to the baseline measurement visit, participants will have a chance to complete several questionnaires in CDART, which will shorten the length of the in-person visit.

At the time of the visit, study staff will review the full study consent in detail before standardized data collection begins. The study participant will be given as much time as needed to review the consent form and ask any questions prior to signing it. Participants will be informed that participation in the study is voluntary and they are free to withdraw their consent and discontinue participation in this research at any time. Study staff obtaining consent will utilize the tailored *Consent Comprehension Checklist* to guide a conversation with the participant that aims to ensure that she or he understands what she or he is consenting to and the nature of informed consent itself.

### **COVID-19 PROVISIONS – VIRTUAL VISITS:**

*Newly enrolled participants will be emailed the full consent form so that they may review it in detail. Then during a subsequent phone or Zoom call, the consent form will be reviewed verbally in detail by the Study Coordinator and participants will be given time to ask any questions and have these questions answered. Participants will be able to indicate their*

*consent using an electronic Qualtrics Survey in which they can indicate whether or not they agree to participate in the study as a whole as well as the stool kit collection and physical activity tracking opportunities. This consent process will include consent to complete online forms and thus will eliminate the use of the previous Qualtrics survey that allowed participants to complete online forms ahead of their in-person visits.*

*Follow-up participants. These participants will be emailed a link to the revised consent addendum so that they may review it in detail. The study coordinator will discuss the changes to the study with already enrolled participants and go through the consent addendum in detail via a phone or Zoom call. They will be able to indicate their consent to participate in the revised virtual study online.*

*Once participants have indicated their consent, they will be mailed their virtual measurement visit package and can begin all elements of the study visit.*

Following consent, participants may be involuntarily withdrawn from the study per the investigator's discretion, if they develop a serious condition that would render participation unwise, including difficulties with glycemic control, and serious physical or psychiatric conditions. Females who become pregnant will also be withdrawn from study participation.

## **Protections against Risk**

All institutions associated with this study are experienced with handling sensitive and confidential data. Certain routine administrative, personnel, physical security, information management, and computer system or network security practices are always in place given the policies and the requirements for safeguards consistent with the management of PHI at both clinical sites. All PHI will be used or disclosed in compliance with the Health Insurance Portability and Accountability Act (HIPAA). Paper forms will be kept in locked files when not in use. Participants will be assigned identification numbers in lieu of names on data management and data analysis files. A master list of identification numbers and names will be kept separate from all database files and will be maintained in a password-protected file that is accessible only to authorized staff at the respective clinical sites. Upon completion of the study, these files will be destroyed. No individual PHI will be used in reports or manuscripts. Data entered and stored on the microcomputer will be archived daily. The data collectors will follow a strict written protocol that describes study measures for protecting data privacy. Patients always have the right to refuse to participate or to refuse to answer any individual question they might find objectionable.

Each site has a highly experienced endocrinologist as part of the local investigative team (UNC – [name]; Stanford – [name]). To minimize the possibility of risks associated with the blood draw, experienced medical staff will obtain the blood samples. A local numbing medicine may be placed on the skin before the blood is drawn to decrease any pain. Participants who have a history of fainting or who develop symptoms of light-headedness will be placed in the supine position. The study physicians will review all laboratory findings for study participants in a timely fashion. Research staff will have guidance (“alert values”) for when to proactively contact the study physician for guidance.

## Hemoglobin A1C

The minimum amount of blood/plasma necessary to conduct these tests will be collected and the total amount collected will not exceed standard, weight-specific guidelines. Blood volumes will be approximately 22 ml at the baseline visit and 12 ml at the follow-up visits. Stored blood will be saved for 10 years after the end of the study. The following table describes the amount of blood required for the laboratory tests.

The minimum amount of blood/plasma necessary to conduct these tests will be collected and the total amount collected will not exceed standard, weight-specific guidelines. Blood volumes will be approximately 22 ml at the baseline visit and 12 ml at the follow-up visits. Stored blood will be saved for 10 years after the end of the study. The following table describes the amount of blood required for the laboratory tests.

MEASUREMENT	Baseline Blood Draw Volume	Remaining Visits Blood Draw Volume
Hemoglobin A1c	2 ml	2 ml
Stored plasma	10 ml	10 ml
Stored whole blood for DNA	10 ml	N/A
Total maximum blood volume	22 ml	12 ml

## COVID-19 Provisions-Virtual Visits

MEASUREMENT	Baseline Blood Draw Volume	Remaining Visits Blood Draw Volume
Hemoglobin A1c	2 ml	2 ml

For the SMART pilot, the interventionists (Registered Dietitians) and study physicians will communicate regularly (verbally and in writing per protocol) regarding glucose control so that any changes in medical management can be made in a timely fashion, as it is understood that with weight loss, adjustments in medical management will be needed.

Study personnel will be trained to identify the signs and symptoms of a blood glucose level that is low or high. They will also be trained to check the blood glucose level, using a glucometer. If low blood glucose occurs during a study visit (< 70 mg/dL), study personnel will be trained to administer 15 grams of an oral carbohydrate, and to repeat as needed every 15 minutes until the blood glucose level is > 70 mg/dL. If the blood glucose level is above 300 mg/dL during a study visit, study personnel will be trained to check for urinary ketones. In cases of low or high glucose levels (with or without the presence of ketones), additional medical interventions may sometimes be

needed. Local policies dictate these procedures, which may include a one-time adjustment in the dose of insulin taken and/or the administration of glucose gel, glucagon, or intravenous glucose. If participants experience hypoglycemia or hyperglycemia outside of study visits, they will be advised to treat these situations per their usual diabetes care plan.

***COVID-19 Virtual Visit Provisions:*** *We are no longer asking participants to report their blood sugar or whether or not they have had anything to eat in the last 8 hours. The only fields of the ‘specimen collection form’ that we will complete are those that pertain to the HbA1c collection, that is, time and date of collection along with any problems the participant may have had.*

At each study visit and RD check-in call, hypoglycemia events will be reviewed with the participant. Participants will be asked to notify the study team within 48 hours of any severe hypoglycemic event (seizure, coma, or need for glucagon administration).

Participants will be completing a CES-D form at all the measurement visits. Although the CES-D is not considered a diagnostic tool for the identification of clinical depression, it is designed to identify people who may be suffering from a depressed mood. Whenever a participant scores high (> 24) on the CES-D, study personnel will inform the participant that the CES-D score is “high” compared to what would be expected for most adults, indicating that the participant may be clinically depressed. If the participant is currently receiving mental health counseling or treatment, study personnel will recommend follow-up with his/her mental health provider. If the participant is not being treated by a mental health provider, study personnel will make a referral based on local guidelines and procedures.

DXA scanning is performed by a certified radiology technologist, knowledgeable in the procedure and equipment. Female participants will undergo a urinalysis pregnancy test prior to each DXA scan to protect the unborn fetus from radiation exposure.

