Study Duration	
Each subject's participation will last approximately 10.5 months.

	Study data collection is expected to end by November 2020. Grant funding ends April 2021.
Study Phases	1. Screening : screening for eligibility, recruiting and obtaining consent 2. Intervention : study intervention (randomization to diets) (Note: Each clinical site will recruit approximately four participants a month over 12 months. Intervention will be ongoing once enrollment has begun.)
Efficacy Evaluations	Glycemic control: HbA1c and percent time in hypoglycemia (continuous glucose monitor worn for 14-days at each measurement visit). Change in weight.
Safety Evaluations	Participants will be asked about hypoglycemic events at each study visit and RD session (in person and telephone). The RDs will communicate regularly with the study endocrinologist to review labs and self-monitored blood glucose (SMBG) data to ensure appropriate insulin dosing.
Statistical and Analytic Plan	We will primarily compare the 3-month response rates to each of the 3 initial diets using standard statistical comparison procedures (e.g., t-tests and ANOVA) for differences in glycemic control (HbA1c and percent time in hypoglycemia) and change in weight.  In addition, we will conduct a series of secondary, hypothesis-generating analyses using standard statistical approaches as well as more complex fixed and mixed effect regression methods such as generalized additive models and random forests for these outcomes plus body fat and fat free mass.
Data and Safety Monitoring Plan	Data quality and safety monitoring will occur both within the research team (data quality committee) (monthly) and a 4-member DSMB (to meet twice yearly).  Participant accrual and retention, progress, completeness of standardized measures, and attendance at intervention sessions will be monitored. All aspects of data collection and data storage will be carefully monitored to ensure rapid detection of errors, inconsistencies or other problems. Distributions of key variables will be monitored for data quality and safety. AE and SAE, as defined by NIH, will be reported to the local site investigator and corresponding IRBs. AE/SAEs will be reviewed monthly.

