**Summary of changes related to COVID-19 Provisions, submitted with Protocol Version 7:**

As of April 2020, we are transitioning the entire study to a virtual format. All follow-up visits will be conducted virtually, and we will continue to enroll new subjects remotely as well. We are making changes according to the following table, described in detail in the protocol document:

Data element	Method and timepoint conducted previously	Method and timepoint conducted now	Major changes
Anthropometrics			
Height	In-person, all visits	At home, baseline only	For existing participants, will use baseline height (avg of 2 closest). For new participants, the home height procedures (Section 8a) will be used.
Weight	In-person, all visits	At home, all visits	Participants will use their BodyTrace scale provided as part of their study participation to measure their weight

			according to the home weight procedures (Section 8a).
Waist circumference	In-person, all visits	At home, all visits	Participants will be mailed a tape measure and provided with instructions as to how to collect this measurement at home (Section 8e).
Lab-based			
HbA1c	In-person, all visits	At home, all visits	At home collection kits will be used (Section 8a).
Fasting stored blood	In-person if fasting and consented, all visits	No longer collecting	This was not a primary outcome measure and is not feasible to collect at home (Section 8e).
Stool sample collection/storage (gut microbiome)	Kit offered for home collection at baseline, Meas 2, Meas 3, and Meas 4	Kit shipped for home collection, Baseline, Meas 2, Meas 3, and Meas 4	The only change to procedure is that the kit will be shipped directly to participants and they will receive their instructions remotely (Section 8e).
BG/Ketones			
Blood ketones	Weekly at-home monitoring by participants on low-carb diet	No longer collection	Participants have not been doing data collection for the most part and this data is not essential for outcomes (Section 8e).

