### **Exclusion criteria**

The following individuals will be excluded from study participation: individuals with other serious metabolic disorders that would render participation unwise, diagnosed eating disorder, or those with other serious conditions that renders participation inappropriate. Individuals who have experienced DKA or severe hypoglycemia requiring outside assistance in the past 6 months will be excluded. Females who are currently pregnant, breastfeeding, planning to become pregnant during the study period or who have delivered a baby in the last 12 months will be excluded. Individuals who are unwilling to follow any of the three study diets will be excluded. Individuals who are unwilling to self-monitor blood glucose levels at least three times a day will be excluded. Individuals who have lost 10 or more pounds in the last 6 months will be excluded.

Medical records will be used to identify patients who potentially meet the eligibility criteria for this study. Medical records will also be used to collect information related to the participant's diabetes care, as well as demographic information. For individuals contacting us about study participation, medical record review will not be required; instead, we will rely on self-report of relevant screening criteria.

Participants may reach out to us after seeing the study on Join the Conquest or through another Type 1 diabetes support network. We will work with NC TraCS to establish recruitment through MyChart.

***Strategies to Optimize Recruitment and Retention:*** Study staff at UNC-CH and Stanford will be responsible for local recruitment activities. Recruitment will use a combination of targeted mailings/emails with phone follow-up and in-person clinic-based strategies. Our recruitment process will utilize the highly successful two-step recruitment strategy used in the FLEX study, consisting of sending an informative recruitment letter/email to eligible participants and following with a series of phone calls by research staff.

***COVID-19 VIRTUAL VISIT TRANSITION (4/2020)*** - All recruitment of new subjects will be conducted electronically. The protocol has been altered to reflect this.

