Fasting blood will be collected at each study visit to allow for storage of blood and plasma for future testing. Samples will be stored for future testing of lipids and other analyses. We will also include storage of whole blood from the baseline visit only for future DNA/genetics work.

**COVID-19 PROVISIONS-VIRTUAL VISITS:** *With the transition to virtual visits, fasting blood and plasma for storage will no longer be collected.*

Participants will complete at home stool collection after the Baseline (Measurement 1) Visit and Measurement Visit 2. Stool samples will be analyzed using 16s rRNA sequencing and analysis of short chain fatty acids using liquid-chromatography mass-spectrometry.

**COVID-19 PROVISIONS-VIRTUAL VISITS:** *Participants who have not taken antibiotics in the past 4 weeks will still be eligible to complete a stool sample at the time of the baseline and measurement visit 2. The stool kits and written instructions with step-by-step photographed procedures will be mailed directly to participants and further instructions will may be provided remotely, through a phone/zoom call.*

Participants on the low carbohydrate diet may be asked to check their blood ketones once weekly using the Nova Max® Plus glucose monitoring system, along with Nova Max ketone testing strips, provided by the study. **Note: as of 4/2020**, the study is discontinuing weekly checks of blood ketones for participants on the low carbohydrate diet due to lack of participation by study participants.

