3=Probably Related	2 = Medical/surgical intervention	3 = Recovered with major sequelae
4=Definitely Related	3 = Hospitalization	4 = Condition still present and under treatment
5=Diabetes Related; Definitely Unrelated	4 = Other (specify under comments)	5 = Condition continues to worsen
		6 = Patient died

All AEs will be reviewed by the study Data and Safety Monitoring Board to determine if an AE is related to the research project. Our team will file a written report to the site IRBs in accordance with local IRB requirements, and to NIDDK. Outcomes for AE's will be monitored by the DSMB and outcome information will be entered into a log for inclusion in reports to participating IRBs and NIDDK as required.

Anticipated events relative to the population under study (e.g., low or high blood glucose) or relative to study activities (e.g., fainting associated with venipuncture) will be noted as potential risks on the informed consent form. The DSMB will also monitor the occurrence of these events. In addition, resource and referral listings for community services will also be provided on a routine basis as needed. Drs. [name] and [name] will also work extensively with the staff at each of the clinics to ensure that if participants need to be referred, these situations are managed in a manner consistent with clinic preferences/policies.

Should any other problems or concerns arise with the data collection or intervention program, the PI or local clinical PI will be available to address these.

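### Ketoacidosis excludes entry alongside severe hypoglycemia, but on study it has no named question at contacts and no participant notification rule

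*Protocol*

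**What the plan says.** Section 5 of the protocol bars both events together: "Individuals who have experienced DKA or severe hypoglycemia requiring outside assistance in the past 6 months will be excluded".

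For conduct on study, the Synopsis (Safety Evaluations) states: "Participants will be asked about hypoglycemic events at each study visit and RD session". Section 12 repeats it: "At each study visit and RD check-in call, hypoglycemia events will be reviewed with the participant". Section 8a has the dietitian ask about severe and non-severe hypoglycemia at each encounter. The one prompt report requested from participants is also in Section 12: "Participants will be asked to notify the study team within 48 hours of any severe hypoglycemic event".

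For high glucose outside visits, Section 12 refers participants to their usual care plan. Section 14 directs them to their diabetes care provider or the emergency room. Neither asks them to tell the study. Section 14 also names a class of events that the DSMB is to follow: "Anticipated events relative to the population under study (e.g., low or high blood glucose", the latter being its own examples.

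**The concern.** A reader would expect an acute event serious enough to bar entry to be actively looked for once diets are assigned. One of the two barred events is sought at every contact and has a 48-hour reporting request. The other has neither, in a trial that includes a low-carbohydrate diet and allows the diet to change at 3 and 6 months.

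Two things are at stake. First, a DSMB count that sets solicited hypoglycemia beside largely unsolicited DKA could be misread, because a low DKA count may only mean that nobody asked. Second, an event learned of late is harder to assign to the diet being followed when it happened.

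**Working it through.** The plan gives no figure to reproduce, so the check sets the passages side by side and then computes delays from the schedule.

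**How each event reaches the study**

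| Step | Severe hypoglycemia | DKA |
|---|---|---|
| Bars entry (Section 5) | Yes | Yes |
| Named for review at each visit and RD contact (Synopsis, 8a, 12) | Yes | No |
| Participant asked to report within 48 hours (12) | Yes | No |
| Open RD question on glucose-management difficulties (9b, 9c) | Could capture | Could capture; not named |
| RD and endocrinologist review of labs and self-monitored glucose (Synopsis) | Could capture | Could capture; not named |
| Forms at Visits 2 to 4 (8e Health History Follow-Up; 8f Diet Acceptability Long Form) | Long form covers hypoglycemia | Not named in the description; items not shown |
| Staff SAE report, typically 24 to 48 hours (14) | If criteria met and staff know | If criteria met and staff know |

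The last row needs care. An inpatient admission for DKA meets the SAE definition, but the reporting interval applies to coordinators and cannot start before they know of the event. An episode that is neither admitted nor otherwise serious falls back on the AE definition, which is limited to unanticipated occurrences, whereas the same section lists high glucose as anticipated. Such an episode may therefore not be logged.

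**Possible delay**

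Input: the Appendix 1 Study Timeline, which has 4 measurement visits and 8 + 15 = 23 RD contacts. (Section 9c gives a total of 18 sessions, but its own parts also sum to 23.) One month is taken as 30.44 days.

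- Longest gap between any two contacts, 2 weeks to 1 month: 30.44 − 14 = 16.4 days.
- Longest gap between RD contacts, 2.5 to 3.5 months: 1.0 × 30.44 = 30.4 days.
- Longest gap between longer RD sessions, for example 1 to 3.5 months: 2.5 × 30.44 = 76.1 days.
- Gap between measurement visits: baseline (day −14) to 3 months is 14 + 3 × 30.44 = 105.3 days; 3 to 6.5 months and 6.5 to 10 months are each 3.5 × 30.44 = 106.5 days.

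So the delay is about 2 to 4 weeks if the open question is put at every RD contact and elicits the event. It is up to about 2.5 months if that question is put only at the longer sessions, and about 3.5 months if a visit form is the first thing to catch it. The SAP says that the duration of diet periods varied widely during the pandemic, so some visit gaps will have been longer. The comparison for severe hypoglycemia is 48 hours.

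**The case against.** The case against is substantial. Several routes could bring a DKA episode to light, and an episode is plainly a difficulty with glucose management. Section 14 provides a relatedness code for diabetes-related events and monthly AE review, and the intervention materials teach recognition of DKA. Hypoglycemia has reasons of its own to be asked about repeatedly: it is part of a co-primary outcome, and a self-reported increase triggers re-randomization. An entry exclusion does not oblige the same question on study. The contact and health-history forms are not in the documents, so they may already contain a DKA item.

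All of this limits the point without removing it. Teaching recognition is not asking for a report, and a form that nobody outside the team can see is not a stated rule.

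Four stronger readings are tempting, and the documents do not support them.

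- That DKA is never asked about or promptly reported. The open questions and the SAE route exist.
- That an event would normally stay unknown for months. This requires every other route to fail, with contacts at most about 16 days apart.
- That stopping the weekly ketone checks opened the gap. Section 8e says "the study is discontinuing weekly checks of blood ketones for participants on the low carbohydrate diet", but those checks were optional and confined to one diet, and the Version 7 change table explains: "Participants have not been doing data collection for the most part and this data is not essential for outcomes". Little detection was lost. A visit-based check remains in Section 12 ("study personnel will be trained to check for urinary ketones"), although it was written for staff at a visit with glucose above 300 mg/dL and visits are now remote.
- That better capture would let the DSMB compare DKA between diets. With 68 participants (SAP) and three starting diets, 68/3 is about 23 each, and participants may change diet twice. A comparison of a rare event would not be informative even with complete capture.

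**Conclusion.** The point holds as a gap in ascertainment, not as a contradiction between passages. As written, the plan gives DKA no named question and no participant notification rule, while it gives both to the event that it treats as equivalent at entry. Capture depends on general questions, periodic forms and staff learning of an admission, and episodes without admission are the most likely to be missed.

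The size is a delay of about 2 to 4 weeks in the favorable case and about 3.5 months at worst on the planned schedule, against 48 hours. The documents give no DKA rate, so no expected number of missed events can be stated, and the conclusion does not need one. It assumes that the unseen forms contain no explicit DKA item. If they do, the remedy reduces to saying so in the protocol and adding the notification request. This is a worthwhile, inexpensive safety improvement; it does not bear on the primary efficacy analysis.

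**What to change.** In the Synopsis (Safety Evaluations) and Section 12, add DKA, and hospital or emergency care for high glucose, to the events asked about at each visit and RD contact and to the 48-hour notification request. Carry the same wording into the Section 8a query. State in Section 14 that these events are logged whether or not they were anticipated and whether or not they led to admission. List them for the DSMB by the diet followed at the time, descriptively and without a between-diet test.

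The cost is one added question per contact and one line in the participant instructions. No treatment rule changes.

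The protocol expected data collection to end by November 2020 and the SAP is dated January 2022. If collection is complete, the change belongs in the follow-on trial, and reports of this pilot should say that DKA was not specifically solicited, unless the forms show otherwise.
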